### 1.3 Rationale for Selection of Investigational Product or Intervention

The same mice studies noted above also evaluated the use of an angiotensin II receptor 1 (AT1R) antagonist losartan, a commonly used anti-hypertensive medication that reduces TGF- $\beta$ 1 activity in other non-CTD disease models due to the extensive cross-talk between the shared elements of the TGF- $\beta$ 1 and AT1R pathways (56). Activation of either TGF- $\beta$ 1R or AT1R results in the phosphorylation of SMAD2/3, leading to transcription of several products inclusive of TGF- $\beta$ 1 itself; further activation of either pathway leads to activation of the ras homolog gene family, member A (RhoA) and contraction of vascular smooth muscle fibers (56). Similar to treatment with nAb, the use of losartan in the *Fbn1*C1030G+ and *mdx* mouse models normalized the aortic root architecture, reduced SMAD2 phosphorylation and translocation, and attenuated evidence of fibrosis in their respective models (46, 47). Additional theoretical advantages of the use of AT1R inhibition via the use of losartan are the potential beneficial effects obtained by biasing angiotensin-based signaling towards the angiotensin II receptor 2 (AT2R). AT2R receptor

signaling appears to anti-inflammatory effects, and the use of renin-angiotensin system (RAS) blockade in humans with MFS has already been attempted (57, 58). In these studies beneficial effects having been noted with the use of angiotensin-converting enzyme inhibitors (ACEI) and ARBs, which have demonstrated reduced aortic root diameter in a small, randomized trial and retrospective analysis, respectively (59, 60). Some controversy has been noted; there has been a potential association between excess AT2R signaling, as would be expected with the use of an ARB like losartan, and the cystic medial degeneration that is seen in aortic aneurysm. This is based upon an *in vitro* study utilizing samples from patients with MFS with end-stage aneurysms, which demonstrated vascular smooth muscle cell apoptosis, which was worsened with ARB use (61). However, Habashi *et al.* later demonstrated worsening aortic root dilation in double knockout mice lack both the fibrillin and AT2R genes, implying a further beneficial effect of AT2R beyond the anti-inflammatory effects noted above as opposed to the hypothetical, perilous effect implied by the *in vitro* study of patients with MFS (62).

#### 1.4 Preclinical Experience

Herein we propose that reducing TGF- $\beta$ 1 activity with losartan in patients with EoE will lead to reductions in the eosinophilia, fibrosis, and smooth muscle contractility that each play a role in the pathogenesis and symptomatology of this disease. While the use of losartan has not been studied to date in either pediatric or adult EoE, it does represent a medication with support of mechanistic data which suggest it as a suitable target for pharmacologic intervention. TGF- $\beta$ 1 expression is increased in the esophageal biopsies of EoE patients relative to normal controls, and in CTD patient populations there is an increased risk of EoE (MFS, EDS, LDS, etc.) (19, 21-23, 41, 42, 45, 63). As losartan is already used in both pediatric and adult populations for hypertension and proteinuria, it represents a unique medication to potentially treat EoE across a broad range of ages. Further, the use of a once-a-day, oral medication, without the difficulties associated with either steroid medications or dietary modification, could provide improved compliance and quality of life for this patient population. We hypothesize that we will see beneficial effects in terms of esophageal pathology within the study period, as the beneficial effect upon aortic root dilation was noted within 36 weeks with the use of the ACEI (enalapril (60)), and within 12 months with the use of an ARB (losartan (59)). This proposal represents the first exploratory prospective study to evaluate the effects of an ARB in EoE, while simultaneously differentiating between EoE vs. EoE-CTD. Though some controversy exists with the use of an ARB vs. ACEI in patients with MFS, both of these drug classes have excellent safety profiles, and both classes are currently in use clinically for these patients. In addition, losartan has been in use for treatment of hypertension for over a decade, and there are clinical trials utilizing losartan long-term in the MFS population without evidence of unusual AEs reported to date. Therefore, we do not have an expectation of AEs that would uniquely be present with the EoE patient population. It is our hope and expectation that this study will demonstrate the clinical value of losartan without evidence of adverse effects.

## 1.5 Treatment with Losartan

Although losartan is most commonly used for treatment of systemic hypertension, it is also routinely used without significant AEs for treatment of normotensive patients with proteinuria (64, 65). Losartan has a negligible effect on resting blood pressure and heart rate in healthy volunteers (66-68).

Losartan is generally well-tolerated for the treatment of hypertension and proteinuria in adult and pediatric patients. However, the current prescribing information for losartan does not provide information regarding the use in patients less than five-years-old (69). The use of losartan is approved and indicated for hypertensive pediatric patients  $\geq 6$  of age with a typical starting dose of 0.7 mg/kg once daily. Currently, the losartan prescribing information (09/2014 Revision) indicates that the adverse event profile for pediatric patients mirrors that of adult patients (69). The approval described in the prescribing information was most likely based in part based upon the outcome of the use of losartan in 177 pediatric patients with hypertension aged between 6-18 years old. While the prescribing information does indeed indicate that 177 patients were consented into the study, two patients were actually re-randomized in the study, for a genuine total of 175 pediatric patients (70). Further, while this report describes patients aged between 6-16 years old, 4 patients less than 6-years-old were enrolled in the study [See Table 1, Ref. (70)]. In spite of the conflict between the prescribing information and the Merck study, losartan remains in regular use for the treatment of both hypertension and proteinuria in pediatric patients. The AEs described in the study are consistent with those described in other studies, and in the current protocol, we intend to monitor the common AEs noted in this and other studies that have evaluated losartan [See Study Stopping Rules, See section [10.5](#)].

The use of losartan in 18 pediatric subjects with Marfan's syndrome significantly slowed the rate of progressive aortic-root dilation and supports our proposal to treat subjects as young as 5 years of age. In the small Marfan's study, no adverse events or side effects were documented among subjects while receiving ARB therapy (59). In pediatric patients, the largest randomized control trial to date evaluated losartan vs. amlodipine/placebo in 411 subjects with proteinuria (with or without hypertension), who were 1-17 years old at the time of entry (71). Of these subjects, 33 were less than six-years old and were treated with losartan alone over the course of 12 weeks [See Table 1, Ref. (71)]. Adverse events (AE) were followed for all subjects in the study, with n=7 (4.6%) having a serious adverse event (SAE) for those being treated with losartan [See Table 2, Ref. (71)]. None of these SAEs were associated with drug. Eight (5.3%) drug-related AE were noted. No patients in the study were discontinued due to a drug-related AE [See Table 2, Ref. (71)]. While renal dysfunction [reduced glomerular filtration rate (GFR)] was noted for two of the patients treated with losartan, this was no different than the amlodipine/placebo group, and losartan was not stopped. In addition, hypotension was noted for one patient treated with losartan but did not result in stopping of the drug. Dosing of losartan is identical for that proposed for the current study, although a maximum limit is not provided, whereas a maximum of 100 mg is planned for the current study.

In a separate one-year longitudinal study of 52 subjects with proteinuria treated with losartan, the reasons for discontinuation were noted and described. These subjects were aged between 3.73 to 17.99 years. The reasons for discontinuation included elevated serum creatinine/potassium, blurred vision, syncope / dizziness, unexplained fatigue, ineffectiveness, or resolution of proteinuria. No SAEs were mentioned in the article (64).

In a similar study by the same authors, 45 patients aged between 3.7-17.9 years old with hypertension treated with losartan, a single SAE associated with the use of losartan was noted (65). However, this occurred in a patient being simultaneously treated with an angiotensin converting enzyme inhibitor (ACEI) and losartan. This patient had pre-existing renal insufficiency and history of borderline high serum potassium, and had septic shock, acute oliguria, and severe hyperkalemia ( $K^+ 7.6$  mEq/L)(65). As a consequence, the authors no longer allow the simultaneous use of an ARB or ACEI in patients, especially if there is evidence of renal insufficiency.

As this current study proposal was originally designed, renal insufficiency was excluded via evaluation of serum creatinine (exclusion criteria 5) and the use of common antihypertension medications ACE, ARB,  $\beta$ -blockers is disallowed in exclusion criteria 12.

## 1.6 Clinical Studies

Losartan has been in use for treatment of hypertension for over a decade, and there are clinical trials utilizing losartan long-term in the MFS population without evidence of unusual AEs reported to date. Thus, we do not have an expectation of AEs that would uniquely be present within the EoE patient population. It is our hope and expectation that this study will demonstrate the clinical value of losartan without evidence of adverse effects.

## 2 Study Hypotheses/Objectives

### 1. Hypotheses

Inhibition of the TGF- $\beta$ 1 pathway could provide a unique means of improving patient care in EoE via the reduction in smooth muscle contraction mediated by the deep-lying mast cells and TGF- $\beta$ 1, as well as reducing pathologic fibrosis and cellular proliferation seen in these patients. Herein we propose that a reduction in TGF- $\beta$ 1 activity via losartan in patients with EoE will lead to reduced eosinophilia, fibrosis, and smooth muscle contractility, which each play a role in the pathogenesis and symptomatology of this disease. Further, the use of a once-a-day oral medication, without the difficulties associated with either steroid medications or dietary modification, could provide improved compliance and quality of life for this patient population. This represents a preliminary descriptive study in which the impact of losartan therapy in patients with EoE or EoE-CTD is assessed.

### 2. Primary Objective(s)

The primary objective of this open-label pilot study is to assess the effect of losartan on the reduction of esophageal eosinophils in participants with EoE with or without a CTD.

### 2.3 Secondary Objective(s)

- To evaluate the effect of losartan on the levels of TGF- $\beta$  and markers of pathway activity in the blood and esophagus.
- To investigate the effect of losartan on the normalization of the EoE transcriptome in participants with EoE with or without a CTD.
- To evaluate the effect of losartan on general histology of the esophagus, using a histology scoring scale.
- To determine the safety of losartan in participants with EoE with or without a CTD.
- To evaluate the effect of losartan by utilizing PROquestionnaires to assess for clinical symptom response.
- To evaluate the effect of losartan by utilizing the histology scoring system created to express the severity and extent of gastrointestinal abnormalities that often accompany eosinophilic inflammation.
- To evaluate the effect of losartan on esophageal compliance through the use of EndoFLIP.

[figure not shown]
## 3 Study Design

### 3.1 Description of Study Design

This is a phase II, open-label trial of losartan in patients diagnosed with EoE with or without a CTD. Prior to entry, patients must meet the current consensus criteria for EoE, in which efforts are made to rule out other causes of esophageal eosinophilia. The trial will perform a preliminary assessment of the effect of the maximum tolerated dose of losartan in participants with active EoE as determined by the absence of side effects and by vital signs being within normal limits. The primary endpoint of the study is the reduction in the number of esophageal eosinophils in participants who will receive losartan orally once a day (Figure 2). The primary safety endpoint is descriptive, and will require reporting of SAE or Grade 3 and above AEs.

NIH Approved 12/06/18

### 3.2 Figure 2: Study design

**Figure 2:** Schematic of study design demonstrating the flow of participants through different stages of the protocol

### 3. Primary Endpoint(s)/Outcome(s)

- Change from baseline in the peak esophageal eosinophil count in participants receiving losartan potassium at the end-of-treatment (EOT) visit (or at early withdrawal) as determined by esophagogastroduodenoscopy (EGD) with biopsy and reported as eosinophils per high-power field (eosinophils/HPF).
- A primary safety endpoint is also included to monitor for adverse events in the enrolled subjects. Specifically, as a descriptive investigation, any SAE or Grade 3 and above AEs that arise during the conduct of this pilot study will be reported.

### 3.4 Secondary Endpoint(s)/Outcome(s)

- Change from baseline in the blood (serum) and esophageal TGF- $\beta$  levels in participants receiving losartan at the EOT visit (or at early withdrawal) as determined by research blood samples and EGD with biopsy, respectively.
- Normalization of the EoE transcriptome in participants receiving losartan at the EOT visit (or at early withdrawal) as determined by EGD with biopsy.
- Change from baseline in histopathology in participants receiving losartan at the EOT visit (or at early withdrawal) as determined by EGD with biopsy.
- Change from baseline esophageal compliance in participants receiving losartan at the EOT visit (or at early withdrawal) as determined by EndoFLIP.
- Change from baseline PROS (Pediatric Eosinophilic Esophagitis Symptom Severity [PEESS], PedsQL Eosinophilic Esophagitis Module [PedsQL™ EoE], EoE Quality of Life Questionnaire, and EEA) in participants receiving losartan at the EOT visit (or at early withdrawal) as determined by EndoFLIP.

### 3.5 Exploratory Endpoint(s)/Outcome(s)

Serum and esophageal tissue will be collected from all participants at screening and at the EOT visit (or at early withdrawal) for the determination of TGF- $\beta$  levels and eosinophils. Exploratory laboratory tests will be analyzed by the research personnel in the [REDACTED].

Participants are not required to fast prior to the blood draw.

The total volume of blood collected for exploratory laboratory tests will be approximately 17.5 mL per visit (screening and EOT/early withdrawal). At any time during the study, the amount of blood collected from the participants will not exceed 5% of the estimated total blood volume over a 24-hour period per institutional policies. All blood and specimen collection and handling will be done in accordance with the institution's laboratory and infection control policies.

## 4 Selection of Participants and Clinical Sites/Laboratories

### 1. Rationale for Study Population

Participants aged 5 to 25 years with active EoE with or without a CTD will be included in this study. Participants of any gender and any race will be included.

### 2. Inclusion Criteria

Participants must meet all of the following inclusion criteria to be eligible for participation in this study.

1. Written informed consent has been provided by the participant /parent or legal guardian.
2. Participants (of any gender and any race) aged  $\geq 5$  years to  $\leq 25$  years at time of screening.
3. The participant has confirmed, active EoE (within 12 weeks prior to enrollment) as defined by esophageal mucosal eosinophils  $\geq 15$  per HPF (400 x magnification) confirmed by the research pathologist AND fits into one of the following categories:
  - a. Participant has not been diagnosed with and does not display phenotypes suggestive of a CTD, or
  - b. Participant has been diagnosed with a CTD (e.g., MFS, LDS, EDS, or hypermobility syndromes).
4. The participant has been on a high dose of PPI (at least one dose, once daily) for at least 8 weeks prior to a diagnostic endoscopy of EoE without histologic resolution (i.e.,  $\geq 15$  eosinophils/HPF). Due to the variety of doses and various PPIs available, the dose will be confirmed adequate at the discretion of the site PI.  
Note: Participants may continue with their acid reflux therapy as long as the dose remains the same throughout the study.
5. Participant must maintain the same diet, swallowed steroid, and PPI therapies throughout the duration of the study. Participants with active EoE on these therapies may be included in the study, as long as they agree to maintain the same diet, swallowed steroid, and PPI therapies.
6. At the time of study entry, a female participant is eligible if she meets one of the following criteria:

- a. Is of non-childbearing potential (pre-menarchal or surgically sterile with documentation);
- b. Is of childbearing potential with a negative urine pregnancy ( $\beta$ -hCG) prior to enrollment into the study (i.e., at screening) and at each study visit. Subsequently, these participants must agree to use adequate birth control measures (e.g., condom, oral / injectable / subcutaneous contraceptives, intrauterine device, or sexual abstinence) during the study and for at least one month after the last dose of study drug, which will be documented in the source documents.

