## 1 Background and Rationale

### 1.1 Background and Scientific Rationale

Esophagitis represents a complex clinical entity often requiring coordinated care within the fields of both allergy and gastroenterology. EoE is diagnostically defined by revised consensus criteria that in brief require an esophageal-specific level of  $\geq 15$  eosinophils per HPF, as obtained from 2 to 4 biopsies from either the proximal or distal esophagus, that is not mitigated by the use of PPIs (2). Further, features such as response to diet may also be used in establishing the diagnosis. Symptomatically, patients with EoE often complain of dysphagia, vomiting, reflux, food aversions, and frank food impactions (2-4). These patients commonly have diagnoses associated with atopy and other allergic disorders such as IgE-mediated food allergy, asthma, allergic rhinoconjunctivitis, and urticaria. Current treatment modalities center around the use of swallowed steroids therapies with either fluticasone propionate or budesonide, oral steroids, and a variety of restrictive diets that rely upon the use of allergy test results, the empiric avoidance of common food allergens, or the elimination of all antigenic proteins via the use of elemental formulas (5-13). Though all of these treatments are effective, they require continual use or the disease will recrudescence in the majority of patients. For the use of steroids, there is the risk of obesity, adrenal suppression, osteopenia, and steroid-induced diabetes and cataracts. Whereas the dietary restrictions can require significant familial or personal commitment to severe dietary restrictions that are life changing.

[figure not shown]

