## 7 Other Medications

### 7.1 Concomitant Medications

Prior medications, such as acid reflux therapies (including PPIs with or without histamine H2 receptor antagonists) or swallowed corticosteroids (e.g. swallowed fluticasone), may be continued as concomitant medications during the study provided that the dose of the medication remains unchanged during the study period.

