### 7.2 Table 3: Prohibited medications and washout time

Medication	Washout Time Prior to Screening Visit (i.e., Study Entry)
Anti-immunoglobulin E (IgE) mAb	6 months
Methotrexate, cyclosporine, interferon $\alpha$	3 months
Anti-tumor necrosis factor (TNF) mAb	6 months
Other systemic immunosuppressive or immunomodulatory agents	3 months
Angiotensin receptor blocker (ARB)	3 months
Angiotensin-converting enzyme inhibitor (ACEI)	3 months
Beta blocker (BB) therapy	3 months
Calcium-channel blocker	3 months
Other investigational drugs	3 months
Omalizumab	6 months
Anti-IL-5 agents	6 months
Anti-IL-13 agents	6 months
Other investigational drugs or device	1 month

Note: Any changes to the participant's asthma or allergy therapies and other concomitant medications during the study will be documented in the appropriate source documents and case report forms (CRFs).

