  - For those patients who meet the base screening inclusion/exclusion criteria, patients will be considered for evaluation of esophageal compliance via the use of EndoFLIP. EndoFLIP is a SOCEvaluation for esophageal dysmotility, done at the same time as their endoscopy. Patients will undergo consent to retrieve EndoFLIP datasets obtained prior to entry and during this study to assess esophageal compliance.

Note: If the participant is on a current dose of acid reflux therapy (e.g., PPIs and histamine H2 receptor antagonists) or swallowed corticosteroid (e.g. swallowed fluticasone), the participant is permitted to continue the acid reflux therapy or swallowed corticosteroid as long as the dose of the medication remains the same throughout the study. If the participant has had an EGD and biopsies performed at CCHMC or at an outside institution prior to the screening visit, the results of the EGD may be used to determine eligibility if it falls within the 12-week window prior to enrollment. These participants will have all other screening procedures completed at the in-office, screening visit. EGDs performed at an outside institution may be used as baseline if the corresponding pathology report and slides are available and reviewed by the CCHMC research pathologist to determine eligibility. In addition, EoE Endoscopic Reference Score (EREF) will be obtained endoscopies performed at the participating institutions.

Some participants who have been seen at CCHMC or at other institutions may have had research samples, tissue and blood, collected at the time of their EGD for further analysis to occur in the [REDACTED] or in the [REDACTED]. If so, permission to utilize the participants' samples for this study will be obtained at the time of informed consent, and will be transferred to the respective labs under a material transfer agreement. Screening physicals will be performed by trained physicians using the Villefranche criteria, Beighton, and Ghent criteria (79, 80). These are simply guidelines, and a physician can still have the capability to provide a participant with a diagnosis of a CTD if their scores do not fall within the abnormal limits.

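### No period of stable swallowed steroid or diet is required before the baseline EGD, or explicitly between it and entry, so a response to background therapy can be counted in the losartan change

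*Protocol*

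**What the plan says.** Protocol section 4.2, criterion 5, sets the rule for background therapy: "Participant must maintain the same diet, swallowed steroid, and PPI therapies throughout the duration of the study". It then admits people already receiving it: "Participants with active EoE on these therapies may be included in the study, as long as they agree to maintain the same diet", with swallowed steroid and PPI named alongside diet. Section 7.1 repeats the condition for acid-reflux drugs and swallowed corticosteroids, which "may be continued as concomitant medications during the study provided that the dose of the medication remains unchanged during the study period". The screening note in section 8.1 says the same. All of these look forward from the start of the study.

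The protocol looks back where it chose to:

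- Criterion 4 requires PPI "for at least 8 weeks prior to a diagnostic endoscopy of EoE without histologic resolution".
- Table 3 (section 7.2) sets washouts for many drugs, including "Other systemic immunosuppressive or immunomodulatory agents" at 3 months. Swallowed steroid and diet are not in the table.

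The baseline biopsy may come before the screening visit and may be done elsewhere: "the results of the EGD may be used to determine eligibility if it falls within the 12-week window prior to enrollment" (section 8.1).

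Section 1.1 says of swallowed steroids, oral steroids and diets: "Though all of these treatments are effective, they require continual use".

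The SAP (Analysis Populations) limits the primary and secondary analyses to participants who took losartan and kept their baseline EoE treatment. It does not ask how long that treatment had been in place at baseline. Neither document gives a covariate, stratum or sensitivity analysis for background therapy or its duration.

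**The concern.** The primary outcome is each participant's change in peak eosinophil count from the baseline EGD to end of treatment, and everyone takes losartan. Any other cause of a falling count therefore enters the estimate directly.

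A participant who began a swallowed steroid or restrictive diet shortly before the baseline EGD, and then kept to it exactly, meets every written rule. The baseline count can precede most of that therapy's effect, and the Week 16 count follows it. A start after the EGD but before entry has the same effect and is not clearly excluded. A participant who recently reduced a steroid or relaxed a diet creates the opposite problem, because the count may rise on study whatever losartan does.

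At stake are the mean change and the percentage below 15 eos/HPF at Week 16. Protocol section 12.5 says the estimates will be used to power later studies, so a bias here would carry forward.

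**Working it through.** **1. The rules side by side**

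| Therapy | Required before baseline EGD | Required from EGD to entry | Required on study |
|---|---|---|---|
| PPI | At least 8 weeks before a diagnostic endoscopy (criterion 4) | Not explicit | Unchanged |
| Swallowed steroid | None | Not explicit | Unchanged |
| Diet | None | Not explicit | Unchanged |

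The criterion 4 endoscopy is a diagnostic one and need not be the baseline EGD. If the study is taken to begin at screening, the interval from screening to enrollment is covered, but an EGD done before screening still leaves a gap.

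**2. The plan's own figure**

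Inputs from section 12.5 and Table 7: n = 15, SD of change 5 on the square-root scale, two-sided 95% interval. Half-width = t(0.975, 14) × 5/√15 = 2.77, which matches the stated ±2.8. The point does not depend on any error in Table 7.

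**3. Shift in the mean**

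Assume that losartan has no effect and that k of 15 participants respond to recently started background therapy by d square-root units. The spurious mean reduction is k × d/15. Both k and d are assumptions.

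- Fall from 60 to 5 eos/HPF: d = √60 − √5 = 7.75 − 2.24 = 5.51. For k = 1, 2, 3 the shift is 0.37, 0.73, 1.10, or 13%, 27%, 40% of the half-width.
- Fall from 40 to 10 eos/HPF: d = √40 − √10 = 6.32 − 3.16 = 3.16. For k = 2 the shift is 0.42, or 15% of the half-width.

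For a recent reduction in therapy the same formula applies with the sign reversed.

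**4. Chance that the 95% interval excludes zero when losartan does nothing**

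This depends on what the planning SD of 5 describes. If it is the residual SD, the starters also widen the sample SD and hence the interval (simulated mixture: k participants shifted by d, the rest by zero). If it is the total SD, already including the starters, a noncentral t with mean k × d/15 applies.

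| Assumed fall | Starters of 15 | Residual SD 5 | Total SD 5 |
|---|---|---|---|
| 60 to 5 | 1 | about 5% | 5.8% |
| 60 to 5 | 2 | 6.4% | 8.3% |
| 60 to 5 | 3 | 9.1% | 12.5% |
| 40 to 10 | 2 | about 5.5% | about 6% |

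**5. Percentage below 15 eos/HPF**

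Both assumed falls end below 15. Two starters of 15 add 2/15 = 13 points to a combined rate. Section 12.4 estimates the rate within each CTD group, where one starter adds 1/10 = 10 points in the EoE group or 1/5 = 20 points in the EoE-CTD group.

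**The case against.** The best defence is that the natural reading of criterion 5 and section 7.1 is disease that is active despite existing therapy. Section 5.4 adds that endoscopies are done for clinical management, every three to six months or to evaluate a change in therapy, and an EGD timed to judge a therapy is unlikely to fall days after it starts. This makes a very recent start before the EGD less likely. It does not exclude one, because the only test is 15 or more eos/HPF on biopsy, which a specimen taken before the therapy has acted can meet. It also does not address a start after the EGD result and before enrollment, which is arguably the more plausible route.

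The SAP's requirement that baseline treatment be kept does not close the gap. It removes people who change therapy on study, not people who had just started.

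Three stronger readings are tempting, and the documents support none of them:

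- A reader might infer that the bias always favours losartan. That holds for recent starters only; recent reductions act the other way.
- A reader might take 8% and 12.5% as the false-positive rates for two and three starters. Those need SD 5 to be the total SD. If only a few participants shift and the residual SD is 5, the rates are about 6% and 9%, and one starter causes no material inflation.
- A reader might assume the dates needed for a sensitivity analysis are already held. Section 8.1 lists diet history and concomitant medications, but neither it nor Table 4 says that start or change dates are captured.

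It is also fair to say that this is a pilot, not sized for testing and described as preliminary. That limits the weight of the error rates. It does not remove the bias in estimates intended to power later studies.

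**Conclusion.** The gap is real. Following criterion 5 and section 7.1 exactly can put a background-therapy response into the primary change and into the percentage below 15 eos/HPF, and with no control arm the trial cannot separate the two. The direction is in losartan's favour for recent starters and against it for recent reductions.

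The size is conditional, because the number of such participants may be zero and their response is not given. Under the assumed falls, the effect on the test is modest for one to three starters. The effects on the point estimate and on the small-group response percentages are plainer. A reader might infer that the trial's result is in fact biased; the documents show only that the rules allow it. The point merits a change because the remedy is small, not because the expected distortion is known to be large.

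**What to change.** Add to criterion 5, in both the synopsis and section 4.2, that swallowed steroid and diet must have been unchanged for a stated minimum time before the baseline EGD and also since that EGD. The length is for the sponsor to set and justify. A lead-in before the EGD alone would leave the interval of up to 12 weeks to enrollment open.

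If enrollment is complete, record start and change dates with the diet and medication history. Pre-specify in the SAP a repeat of the primary analysis and of the below-15 eos/HPF analysis, excluding participants who do not meet the stability period. Report how many were excluded and whether each had recently started or recently reduced therapy. A count of zero would itself remove this explanation.

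The cost is one eligibility clause or one sensitivity analysis. Some candidates would wait or be excluded, and dates may have to be retrieved from medical records.
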